#### **d. Identification of Subjects**

Describe how you will identify subjects. If you plan to use private records (EHR, Dept. of Licensing) complete 5.e, 5.f., and 5.g below as relevant.

ORIGINAL (In-Person) COHORT:

A KPWA programmer will use KPWA's electronic medical records and other automated data files to identify eligible King County, Washington subjects from virtual warehouse data. (A waiver of consent for this identification method is requested as part of this application.) The programmer will put the variables pulled into a database for recruitment tracking.

Source (specify) (i.e., from KPWA, from an approved or previous study, from another site)	List of electronic data that will be used to identify potential subjects.	Date Range (if relevant)
KPWA VDW	

• KPWA members residing in King County

• Contact information including phone and address

• over age 60 up to age 89;

• BMI <math>\geq 30</math> and <math>< 50 \text{ kg/m}^2</math>;

• not residing in long-term care or skilled nursing and not receiving hospice care; and,

• no diagnosis codes indicating dementia or serious mental illness (e.g., schizophrenia, bipolar disorder), or a terminal or serious illness (e.g., cancer) in the past 2 years or deafness/significant hearing loss.

• Systolic blood pressure <math>> 130</math> two times in previous 12 months (to be used for stratifying at randomization)

• Continuously enrolled at KP for previous 12 months

• No record of death

• Not on the No Contact list

• Primary care at Capitol Hill, Downtown, Northgate, Rainier, Burien, Renton, Federal Way, Factoria or Bellevue - Consumer numbers from the ACT study participants will be accessed in order to make sure these participants are not included in the HART study population

	Jan 2017-present
ACT study records		

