**ORIGINAL (in-person) COHORT**

1. Subjects are contacted by the KPWA survey research team and provide oral consent over the phone in the initial screening and eligibility process; if eligible and interested, subjects will be mailed an activPAL device along with instructions on how to wear it for one week and will be scheduled for their first/baseline visit at KPHR research clinic.
2. **COVID-19 UPDATE: BASELINE VISITS ARE CURRENTLY ON HOLD** Subjects will attend a baseline screening visit at KPHR research clinic in downtown Seattle.
  - a. At the baseline visit, prior to signing the consent form, the RS will ask the potential participant to recap briefly their understanding of the study. Once subjects have signed written, informed consent at the baseline visit they will have baseline measurements taken, including height, weight, waist circumference, physical function and blood pressure. They will have a small amount of blood collected by finger prick. They will turn in their activPAL device to the research specialist. They will also complete a survey containing self-reported scales regarding health symptoms (depressive symptoms, pain, fatigue), daily activities, and psychosocial mediators (e.g. habit strength, self-efficacy). All participants will receive a \$40 incentive for completing measurements at the baseline visit. If participants inquire about their blood values or blood pressure, we will share the information with them but without interpretation and advise them to see their provider if they have questions or concerns.
  - b. After baseline activPALs are returned, participants will be randomized (using a link created by the study biostatistician and programmer) to receive i-STAND (N = 142) or healthy lifestyle control (N = 142). To ensure that baseline sitting time is balanced, we will stratify participants into two groups based on self-reported sitting-time using median sitting time from our pilot work as a cut point: moderate (<8.5 hours/day) and high ( $\geq 8.5$  hours/day). We will also stratify by obesity level (30-35 vs 35+kg/m^2) and

blood pressure (systolic BP over or under 130).

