  - a. During the baseline phone visit, participants will either complete a survey containing self-reported scales regarding health symptoms (depressive symptoms, pain, fatigue), daily activities, and psychosocial mediators (e.g. habit strength, self-efficacy) with the research specialist or will complete the survey online (their preference). Participants will be guided through collecting their waist measurement, weight and blood pressure using the devices and tools sent ahead of time. Per instructions and reminders sent to participants, if they have consumed any caffeine or tobacco, or exercised within 30 minutes of the visit, the visit will be rescheduled. Participants will also be guided through the modified chair sit over the phone. All participants will be mailed a \$30 cash incentive for completing measurements at the baseline visit. If participants inquire about their blood pressure readings, we will advise them to see their provider if they have questions or concerns.
  - b. After baseline activPALs are received by mail, coaches will download the data and participants will be randomized (using a link created by the study biostatistician and programmer) to receive i-STAND (N = 142) or healthy lifestyle control (N = 142). To ensure that baseline sitting time is balanced, we will stratify participants into two groups based on self-reported sitting-time using median sitting time from our pilot work as a cut point: moderate (<8.5 hours/day) and high ( $\geq 8.5$  hours/day). We will also stratify by obesity level (30-35 vs 35+kg/m^2) and blood pressure (systolic BP over or under 130). Coaches will call participants to notify them of their assigned cohort and to schedule their baseline coaching visit. At this time they will also confirm if they prefer to use email or regular mail.

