**Demographics:** Age, sex, education, marital status, race/ethnicity, retirement status, and other pertinent demographics will be measured using self-reported items on the baseline survey. Some demographic variables will be used as covariates in analyses.

**Psychosocial and environmental measures:** We will measure self-efficacy based on modifying measures that were developed in youth and adults (since none exist for older adults) and habit formation which will be assessed using a modification of the Self-Report Habit Index (e.g., "sitting is something I do without thinking").

**COVID-19 UPDATE:** We have added new sections to the surveys with validated instruments to better assess participant psychosocial status in the current environment. This includes lower extremity items from the Late-Life Function and Disability Instrument (LLFDI) for physical function; Generalized Anxiety Disorder Assessment (GAD-2) and the Perceived Stress Scale (PSS) for stress/anxiety; and COVID-19 impact. As always, participants can choose not to answer questions on the survey that make them uncomfortable. This information will be used by the statistician to determine whether any of the COVID-19 related variables are moderators of the interventions.

**Physical function.** The Short Physical Performance Battery (SBBP) will objectively evaluate lower extremity function with tasks for balance, gait speed, and lower-extremity strength (chair rise). Gait speed significantly improved in our prior study. SPPB will also be a covariate as it is associated with sedentarism.

**COVID-19 UPDATE:** Until we resume normal business, we will only be able to measure the chair rise as part of a remote assessment. The study RS will provide instructions and guidance to the participant via phone in order to conduct this measure remotely.

**Other behavior changes.** We will explore other activPAL metrics including sit-to-stand transitions, standing time, and step counts (as a measure of total physical activity). The same data-processing techniques will be used for these outcomes as for activPAL-measured sitting time. Self-reported sedentary behaviors will be assessed with the Sedentary Behavior Questionnaire to understand what types of sedentary behaviors are amenable to change. This measure has acceptable test-retest reliability and convergent validity.

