**a. Data Analysis**

Describe the data analysis plan, including:

- Statistical procedures.
- When applicable, the power analysis.
- Any procedures that will be used for quality control of collected data.

FOR BOTH ORIGINAL AND REMOTE COHORTS: We will add secondary analyses to address changes due to COVID-19.

*Preliminary analyses. The statistician will be blinded to intervention condition and intent-to-treat analyses will be performed.* Before analysis, data will be cleaned and checked for out-of-range and invalid values. We will examine the distribution of baseline covariates across groups to evaluate balance by randomization assignment. Further, we will compare follow-up rates by group assignment along with assessing for imbalance of baseline covariates by intervention group in the subset with follow-up outcome measures. Given the large sample size, we expect that between-group differences will be small. However, if factors differ by group at baseline, we will adjust for them in the final analyses or use them in imputation analyses if we have a larger than expected dropout rate. All analyses will be based on the “intent-to-treat” principle. Regardless of actual intervention participation, outcomes will be analyzed using the group to which participants were randomly assigned. We will also attempt to obtain follow-up data from all participants, regardless of participation level.

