**Aim 1: Determine the efficacy of i-STAND to improve primary and secondary outcomes at 6 months.**

*Primary Outcome Analysis:* Our primary outcomes are change from baseline in mean daily sitting time and systolic and diastolic blood pressure (described in Section C12). We will compare group means for our primary outcomes between participants randomized to i-STAND versus attention control using linear regression with generalized estimating equations (GEEs) including both outcome time points at 3 and 6 months. GEE is used to account for multiple outcomes measured on the same study participant along with relaxing the normality assumption that standard linear regression methods require. We will adjust for baseline covariates including participant age, sex, physical function, and respective baseline outcomes with other covariates that are imbalanced in preliminary analyses. If dropout is above 15%, we will employ imputation techniques to address missing data issues. However, our focus will be on minimizing dropout rates. Analyses for secondary outcomes including lipids, fasting glucose, weight, and waist circumference will be similar, adjusting for respective baseline outcomes in the analysis. *Aim 2: Determine the maintenance of sitting and blood pressure reductions over 12 months.* We will conduct a sequential series of analyses using a similar statistical framework as outlined for Aim 1, but using 12-month follow-up data. We will first run a regression model with three groups (attention control, i-STAND no boosters, and i-STAND with boosters) including baseline covariates as outlined above. We will then

assess differences in primary outcomes at 12 months in the two i-STAND groups: with and without the booster intervention. If a significant difference in a given primary outcome is found in sitting time at 12 months between the i-STAND booster versus no booster groups (Scenario 1), we will further compare the i-STAND booster and no booster groups to the attention control group. Scenario 1 assessments will determine if i-STAND with boosters is better than i-STAND without boosters and if either or both I-STAND groups are better than attention control at 12 months.

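### The primary model names none of the three randomisation strata, and its imbalance rule and physical function covariate are not fixed in advance

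*Combined protocol and SAP*

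**What the plan says.** **Randomisation.** Section 5 (Study Procedures) describes the same stratification for both cohorts. In the Original cohort, "we will stratify participants into two groups based on self-reported sitting-time", cut at 8.5 hours per day. The Remote cohort text repeats this and adds "We will also stratify by obesity level" (30-35 vs 35+ kg/m²) and systolic blood pressure over or under 130; the Original text has the same two factors. Section 4.d shows where the blood pressure factor comes from: health-record systolic readings above 130 "two times in previous 12 months (to be used for stratifying at randomization".

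**Primary model.** Section 5.a, Aim 1, specifies linear regression with GEE on the 3- and 6-month outcomes, and says the analysis will "adjust for baseline covariates including participant age, sex, physical function, and respective baseline outcomes with other covariates that are imbalanced in preliminary analyses". It names no stratification factor and no cohort term.

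**Imbalance rule.** Section 5.a, Preliminary analyses, says "if factors differ by group at baseline, we will adjust for them in the final analyses", or use them for imputation if dropout is larger than expected. It also plans "assessing for imbalance of baseline covariates by intervention group in the subset with follow-up outcome measures". It gives no test, threshold or candidate list.

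**Physical function.** For the Original cohort, section 5 says "SPPB will also be a covariate as it is associated with sedentarism". The Remote cohort has only the chair-rise part of that battery, guided by telephone; sections 4.k and 5 call this test modified. LLFDI lower-extremity questionnaire items are part of the Remote survey, and a COVID-19 update added them to the Original cohort's surveys. Aim 1 does not say which measure is meant.

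**The concern.** Stratified allocation balances the arms on the strata, so the true variance of the treatment difference is smaller than a model without the strata estimates. The reported standard error is then too large and some precision is given away. Robust GEE standard errors do not correct this. The strata are also unlikely to enter through the imbalance rule, because the design balances them.

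The other two gaps concern pre-specification. The primary model takes in whatever is found imbalanced, so it cannot be written down before the data are seen. The physical function covariate cannot be built as one variable for both cohorts from the text as it stands.

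**Working it through.** **1. The plan's own figure.** Inputs from Power calculations in section 5.a: 284 randomised, 15% loss, 241 analysed, SD of change 97 min/day, difference 41 min. Alpha and sidedness are not stated. Two-sided 5% is assumed, because a one-sided test would give about 95% power.

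- SE = 97 × √(4/241) = 12.50 min.
- Power = Φ(41/12.50 − 1.96) = 90.7%.
- By the same formula, systolic (6.2 mmHg, SD 14.7) gives 90.6% and diastolic (4.0 mmHg, SD 9.5) gives 90.5%.

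The stated 90% is reproduced.

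**2. Which strata have a baseline counterpart in which model.**

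| Stratification factor | Sitting model | Systolic model | Diastolic model |
|---|---|---|---|
| Self-reported sitting | activPAL sitting (partial) | none named | none named |
| Obesity level | none named | none named | none named |
| Record-based systolic BP | none named | measured systolic (partial) | measured diastolic (related only) |

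**3. Effect of leaving the strata out.** Let R² be the share of residual variance that the strata explain beyond the named covariates. The documents give no value, so 2% and 5% are assumed. Let B be the share explained by age, sex, physical function and the baseline outcome, assumed to be 0, 20 or 30%, and let s = 12.50 × √(1 − B).

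- True size without strata = 2 × (1 − Φ(1.96/√(1 − R²))) = 4.77% at R² = 2% and 4.43% at 5%.
- Reported SE too large by 1/√(1 − R²) − 1 = 1.0% and 2.6%.
- Power without strata = Φ((41 − 1.96s)/(s√(1 − R²))).
- Power with strata = Φ(41/(s√(1 − R²)) − 1.96).

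| B | R² = 2%: without, with | R² = 5%: without, with |
|---|---|---|
| 0 | 90.90, 91.22 | 91.23, 92.02 |
| 20% | 95.78, 95.95 | 96.02, 96.43 |
| 30% | 97.62, 97.73 | 97.79, 98.05 |

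The loss is 0.1 to 0.8 points. At B = 0, the loss for systolic and diastolic pressure also rounds to 0.3 and 0.8 points. These formulas treat the 6-month contrast as a two-sample comparison, as the plan's own power calculation does.

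A simulation agrees. It used 40,000 trials per setting, eight equal strata, assumed blocks of 4, random loss to 241, and B = 0. For R² of 0, 2 and 5%, size was 4.8, 4.6 and 4.4% without strata and cohort terms, and 4.8% throughout with them. Power was 90.5, 90.8 and 91.0% without, and 90.5, 91.0 and 91.9% with. The Monte Carlo standard error is about 0.1 point for size and 0.15 for power.

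**4. The imbalance rule.** With ten independent candidates (an assumed number), the chance that at least one is flagged is 1 − (1 − p)^10. This is 40% at p<0.05 and 65% at p<0.10. For a standardised difference above 0.1 with 142 per arm, p per covariate is 2 × (1 − Φ(0.1/√(2/142))) = 0.399, which gives 99%. The fitted model therefore depends on a rule that the plan does not state.

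Type I error does not suffer under any one rule. A null simulation (4,000 trials, 241 participants, ten candidates jointly explaining an assumed 20% of variance) gave 5.3% with nothing added, 4.6% for p<0.05, 4.3% for p<0.10 and 3.9% for a standardised difference above 0.1. The Monte Carlo standard error is √(0.05 × 0.95/4,000) = 0.3 point.

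**5. Physical function.** Section 4.a plans 100 Original and 184 Remote participants. If the covariate means the SPPB, it exists by design for 100/284 = 35%; the other 184/284 = 65% have a different test.

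**The case against.** The best defence is that the covariate list is introduced as open, that two of the three strata have a related baseline measure in their own model, and that the effect is small and conservative. All of that stands, and it is why the point is minor. It does not remove the gap: an open list is not a pre-specified model, and obesity level is not represented in any primary model. The R² values are assumptions; if the strata explain nothing further, nothing is lost.

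A reader might infer four stronger things that the documents do not support.

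- *That omitting the strata biases the result or risks a false positive.* It does neither; true size falls below 5%.
- *That the imbalance rule inflates type I error.* Simulated error reaches about 6 to 7% only if the most favourable of four rules is reported after seeing the results. The plan proposes nothing of the kind, and section 5.a blinds the statistician to condition.
- *That it is open which balance check triggers adjustment.* The trigger refers to group differences at baseline, which most naturally means the check in all randomised participants. The check in those followed up is described together with follow-up rates and fits the imputation clause.
- *That the primary analysis will be confined to the 35% with an SPPB.* The sentence making the SPPB a covariate is in the Original cohort section only and is not repeated for the Remote cohort. The supported defect is that Aim 1 does not name the instrument.

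**Conclusion.** The concern holds as a minor precision and pre-specification point. None of the three stratification factors is named in the primary model. Under an assumed R² of 2% or 5%, this makes true size about 4.8% or 4.4% and costs 0.1 to 0.8 points of power. The estimate is unbiased, and N=284 and the 90% power are unaffected. The open imbalance rule matters only because the model is not fixed before the data are seen. The physical function covariate needs a named instrument. The sizes rest on two-sided 5% alpha and on the assumed R², B and simulation settings, none of which the documents give.

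**What to change.** In section 5.a, Aim 1, pre-specify the primary covariates as:

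- the three stratification factors, with the values used at randomisation;
- the baseline value of the outcome, age and sex;
- cohort (Original or Remote);
- baseline chair rise, the one performance measure planned at baseline in both cohorts.

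The Remote chair rise is a modified telephone test, and a cohort main effect absorbs only a difference in level. So either add a cohort-by-chair-rise term or standardise chair rise within cohort. Keep the Original cohort's chair-rise component as a value separate from the SPPB total.

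Move imbalance-driven covariates to a sensitivity analysis with a stated candidate list and threshold, judged in all randomised participants. Leave their role in imputation, under Preliminary analyses, unchanged.

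The cost is SAP wording and a few degrees of freedom out of about 241: three for the strata, one for cohort, and one more if the interaction is used. In the simulation above, strata and cohort terms that explained nothing cost no measurable power (90.5% with and without). The sample size does not change.
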